#### **5.1.2 Formulation, Appearance, Packaging, and Labeling**

Melatonin is a widely sold synthetic molecule in various forms including tablets, gummies and liquid. In the present study, the tablet version of the medication will be used at a dose of 5mg. It will be distributed to patients in a standard pill pack labelled as "Study Drug." Patients will be informed that they will either be taking melatonin or a placebo pill with no chemical activity. Only the research staff involved in the randomization process will know if the patient is in the melatonin arm or the placebo arm. The placebo ingredients are Microcrystalline Cellulose, Silica, Gelatin, Titanium Dioxide, Red #3, and Blue #1.

#### **5.1.3 Product Storage and Stability**

The melatonin and placebo tablets will be stored in the Department of Orthopedic Surgery research offices at [name], in a climate controlled office. As the product does not need to be refrigerated prior to being open there is no need for refrigeration storage. The average expiration date for a bottle of melatonin tablets is more than 1 year from purchase.

#### **5.1.4 Preparation**

There is no special preparation necessary for this product.

#### **5.1.5 Dosing and Administration**

There will be no special administration instructions given to patients, only that they should take one pill in the evening with water within 1 hour of bedtime each night for 14 days.

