#### **4.2 Exclusion Criteria**

An individual who meets any of the following criteria will be excluded from participation in this study:

- Non-elective conversion arthroplasty
- Consistent melatonin use within 1 month of surgery
- Bilateral total joint arthroplasty
- Contraindications to use of melatonin (diabetes, calcium channel blocker use, depression)
- Conditions and medications likely to confound results due to impact on subjective and/or objective sleep quality (insomnia, drug/alcohol abuse, and use of benzodiazepines, and prescription sleep aids)
- Conditions likely to impair capacity to adhere to protocol (mental impairment, psychiatric disorders other than anxiety/depression)

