## **5 Study Agent (Study drug, device, biologic, vaccine etc.) and/or Procedural Intervention**

### **5.1 Study Agent(s) and Control Description**

Melatonin, as previously described, is a widely available over the counter sleep aid.

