### **5.1.8 Tracking of Dose**

Patients will be encouraged to return the empty bottle at the 2 week postoperative visit.

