## **6 Study Procedures and Schedule**

### **6.1 Study Procedures/Evaluations**

#### **6.1.1 Study Specific Procedures**

- Medical history- a patient's medical history will be elicited during their pre-operative indication for surgery by their operative surgeon. This information will be then accessed via the EMR
- Medication history- current medications will be elicited during the patient's pre-operative indication for surgery by their operative surgery. This information will then be accessed via the EMR
- Physical examination- the patient's height and weight at each visit will be recorded, as well as a targeted physical musculoskeletal examination of the affected joint (ie hip for THA and knee for TKA). This information will then be accessed via the EMR
- Pre- and postoperative sleep survey,
- Survey on quality of sleep,
- Sleep diary
  - To be kept every day for the first 2 weeks
- VAS
- Opioid consumption will be measured based on in-patient pain medications given following surgery. This data will be pulled from Epic following discharge.

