### **6.2 Study Schedule**

Procedure	Screening/Visit 1 (SOC visit within - 3 months of surgery)	Surgery	Visit 2 (SOC visit within +2 months of surgery)
-----------	---	---------	--

Screening	X (Research only)		
Consent	X (Research Only)		
Medical History	X (SOC)		
Surgical History	X (SOC)		
Demographics	X (SOC)		
Distribute medication		X (Research Only)	
Collect pill bottle			X (Research Only)
Collect Adverse Events			X (Research Only)
Collect Questionnaires and peri-operative data (in-patient opioid consumption, Epworth and Stanford sleepiness scale, VAS Pain Scale)		X (Research Only)	X (Research Only)
Collect Sleep Diary			X (Research Only)

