#### **Visit 2 (standard of care post-operatively visit within 2 months of surgery)**

- Observe patient's recovery from TJA surgery as per standard of care
- Record participant's adherence to treatment program.
- Record patient standard sleepiness scale, PROMIS – Sleep Disturbance, VAS pain scores, collect sleep diary and opioid consumption.

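### The protocol body does not tell patients to avoid non-study melatonin on days 1-14, and names no source, visit or window that would record its use at home

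*Combined protocol and SAP*

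**What the plan says.** **Entry.** Section 4.2 excludes patients with consistent melatonin use within a month of surgery, and those with insomnia or taking benzodiazepines or prescription sleep aids. It describes the latter group as "Conditions and medications likely to confound results due to impact on subjective and/or objective sleep quality". These are eligibility criteria; section 4.2 does not extend them into the treatment period.

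**Treatment period.** Section 5.1.5 states: "There will be no special administration instructions given to patients, only that they should take one pill in the evening with water", within an hour of bedtime, for 14 nights. Section 5.1 says "Melatonin, as previously described, is a widely available over the counter sleep aid", and section 5.1.2 says "Patients will be informed that they will either be taking melatonin or a placebo pill with no chemical activity".

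**Data capture.** Section 12.1 lists concomitant medications among the clinical data to be entered in RedCap from source documents, and section 9 makes the case report form the primary instrument. The procedures that are named are these:

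- Medication history is taken before surgery (6.1.1, 6.2.2).
- For drugs after surgery, section 6.1.1 says "Opioid consumption will be measured based on in-patient pain medications given following surgery".
- A sleep diary is kept daily for two weeks (6.1.1); its items are not listed.
- Visit 2 records adherence and is to "Record patient standard sleepiness scale, PROMIS – Sleep Disturbance, VAS pain scores, collect sleep diary and opioid consumption". The section 6.2 schedule has no concomitant-medication row.
- Adherence relies on the study bottle (8.4.4): "Patients will be encouraged to return the empty bottle at the 2 week postoperative visit".

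**Analysis.** Section 8.3 analyses all patients as randomised, with the hip and knee cohorts kept separate.

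**The concern.** A placebo patient who sleeps badly after surgery knows that the tested agent is melatonin, knows that the study pill may be inert, and can buy melatonin without a prescription. Section 1.3 places most of the sleep disturbance in the first two weeks, which is the treatment window. Occasional users also remain eligible, since only consistent prior use is excluded.

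The effect on the comparison is not symmetric. Outside melatonin gives a placebo patient the tested agent, whereas it gives a melatonin patient only a higher dose. Such use would therefore tend to pull the two arms together. At stake is how a null result is read: did 5 mg melatonin do little, or did some of the control group take it too? A count of outside users by arm would allow a qualitative judgement on that question. The protocol body neither discourages the use nor says how that count would be obtained.

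**Working it through.** **1. Is there a rule or a named route for days 1-14?** Each place that could supply one was checked.

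| Place | What it covers | Home melatonin, days 1-14? |
|---|---|---|
| 4.2 | Use before surgery | No |
| 5.1.5 | How to take the study pill | No rule on other melatonin |
| 6.1.1, 6.2.2 medication history | Before surgery | No |
| 6.1.1 opioid extract | In-patient pain medication | No |
| 6.1.1 sleep diary | Daily for two weeks | Right period; no medication item named |
| 6.2 schedule; Visit 2 | Scales, pain, opioids, diary, adherence, adverse events | Not named |
| 6.2.5, 7.3 | Unscheduled contacts; adverse events | Not a question about over-the-counter use |
| 8.4.4, 5.1.8 | Study bottle | Counts study pills only |
| 12.1 | Concomitant medications in RedCap | Could include it; no source, visit or window given |

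**2. The plan's own figure.** Inputs from section 8.2: difference 2.65, SD 5.3, two-sided alpha 0.05, power 80%. The standardised difference is 2.65 / 5.3 = 0.50. A two-sample t-test (equivalently a two-group ANOVA) needs 63.8, rounded up to 64 per arm, or 128 per cohort. This matches the plan. Power at 64 per arm is 80.1%, so there is almost no reserve, and section 8.2 makes no allowance for dilution.

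**3. Illustrative dilution.** None of the following three inputs is in the documents; all are assumptions.

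- c = share of patients who take non-study melatonin
- f = share of the full effect that a placebo user gains
- g = gain of a melatonin-arm user relative to a placebo user

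The placebo mean moves by 2.65 × c × f and the melatonin mean by 2.65 × c × f × g, so

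difference = 2.65 × (1 − c × f × (1 − g)).

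Power is for a two-sample t-test with 64 per arm and SD held at 5.3.

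| c | f | g = 0: difference, power | g = 0.5: difference, power |
|---|---|---|---|
| 0 | – | 2.65, 80.1% | 2.65, 80.1% |
| 5% | 0.5 | 2.58, 78.1% | 2.62, 79.2% |
| 10% | 0.5 | 2.52, 76.0% | 2.58, 78.1% |
| 5% | 1 | 2.52, 76.0% | 2.58, 78.1% |
| 10% | 1 | 2.39, 71.4% | 2.52, 76.0% |

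For example, c = 10%, f = 1, g = 0 gives 2.65 × 0.90 = 2.385; with g = 0.5 it gives 2.65 × 0.95 = 2.5175. The g = 0 column covers use in the placebo arm only, or use in the melatonin arm that adds nothing.

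**The case against.** **Capture is planned.** Section 12.1 says concomitant medications will be entered, and section 9 requires all case report form data. This stands. A reader might infer that outside use will go unrecorded, or that a null result could not be told apart from a diluted one. The documents do not support either reading. What is missing is a named source and window for home use, not a plan to collect medication data.

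**The relevant forms are not visible.** The case report form and diary items are not reproduced, and the consent form, which section 11.3.1 says describes the procedures in detail, was not available for review. An avoidance instruction or a diary item on sleep aids could sit there. This also stands, and it limits the point to what the protocol body specifies.

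**Section 5.1.5 concerns how to take the tablet.** It is not a policy on other medication, and the point does not rest on it alone. It is where an avoidance instruction would naturally sit, and no other section of the protocol body supplies one.

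**The size is assumed and modest.** No rate of outside use is given. The lowest figure, 71%, needs 10% of placebo patients to gain the whole 2.65 points with no gain among melatonin-arm users, and 2.65 is a planning value rather than an observed effect of melatonin. The section 4.2 exclusions plausibly remove many patients who would self-treat. All of this stands: the table shows sensitivity, not an expected loss.

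**The planned estimate is not biased for its own question.** A reader might infer that outside use invalidates the primary analysis. It does not: the as-randomised comparison remains valid for the effect of assignment. Recording use would not change that result; only the avoidance instruction can limit dilution.

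**Other sleep aids.** These could be used in both arms and could move the Epworth score either way, so the point is confined to melatonin.

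**Conclusion.** The point holds as a gap in the protocol body that is cheap to close. Non-study melatonin is restricted at entry only, no instruction covers days 1-14, and the planned concomitant-medication data have no named route to home use. Outside use by placebo patients would shrink the contrast and make a null result harder to interpret.

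The size is unknown. Under the assumed rates, the loss is about 2 to 9 percentage points of power if only placebo patients benefit (80% to 78-71%), and about 1 to 4 points if use is equally common in both arms and melatonin-arm users gain half as much (79-76%). These figures rest on the assumed c, f and g, an unchanged SD, and a true melatonin effect equal to the planned 2.65 points. Confidence is medium, because the diary and consent form might already contain the missing items.

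**What to change.** 1. In section 5.1.5, add that patients should take no melatonin other than the study pill through day 14. This is the step that can limit dilution.
2. Add one daily line to the existing 14-day sleep diary asking whether any melatonin other than the study pill was taken that night, with name and dose. Name the diary as a source for the concomitant medications in section 12.1.
3. In section 8.4, report by arm within each joint cohort the number and percentage of patients with any non-study melatonin use, and the number of nights.
4. Keep the as-randomised analysis primary. Do not adjust for users or exclude them: use after randomisation depends on how well the patient is sleeping, so either step would introduce bias.

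If the consent form or diary already contains the instruction or the question, it is enough to cite it in the protocol. The cost is one sentence in 5.1.5, one diary line with a cross-reference in 12.1, and one sentence in 8.4. The downside is slightly more diary burden for patients.

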#### **5.1.6 Route of Administration**

Oral

#### **5.1.7 Duration of Therapy**

Patients will consume melatonin for 2 weeks.

### **5.1.8 Tracking of Dose**

Patients will be encouraged to return the empty bottle at the 2 week postoperative visit.

### **5.2 Study Agent Accountability Procedures**

The study agent, melatonin, and placebo will be stored at the Department of Orthopedic Surgery research office. When the patients are randomized to either arm of the study, the designated agent will be given to the patient at the preoperative visit. At the termination of the project any unused study agent will be destroyed on site in the trash. Any tablets or capsules will be mixed them all together with normal trash and placed in a sealed bag, then placed in a trash bin.

## **6 Study Procedures and Schedule**

### **6.1 Study Procedures/Evaluations**

#### **6.1.1 Study Specific Procedures**

- Medical history- a patient's medical history will be elicited during their pre-operative indication for surgery by their operative surgeon. This information will be then accessed via the EMR
- Medication history- current medications will be elicited during the patient's pre-operative indication for surgery by their operative surgery. This information will then be accessed via the EMR
- Physical examination- the patient's height and weight at each visit will be recorded, as well as a targeted physical musculoskeletal examination of the affected joint (ie hip for THA and knee for TKA). This information will then be accessed via the EMR
- Pre- and postoperative sleep survey,
- Survey on quality of sleep,
- Sleep diary
  - To be kept every day for the first 2 weeks
- VAS
- Opioid consumption will be measured based on in-patient pain medications given following surgery. This data will be pulled from Epic following discharge.

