## Protocol Summary

Title	MELATONIN USE AFTER PRIMARY TOTAL JOINT ARTHROPLASTY: A RANDOMIZED, DOUBLE BLIND, PLACEBO-CONTROLLED TRIAL
Brief Summary	The purpose of this study is to determine the effect of melatonin supplementation on patient sleep quality, length of stay, and opioid consumption following primary, unilateral, elective total hip or knee arthroplasty.
Phase	N/A
Objectives	The primary objective is improved sleep quality postoperatively
Methodology	Single Center, randomized, double-blind, placebo-controlled clinical trial
Endpoint	The primary endpoint will be enrollment and completion of the study of 256 patients as pre-determined by statistical analysis.
Study Duration	Approximately 12 months (post IRB approvals)
Participant Duration	We estimate each patient will need to participate for roughly 60 days
Duration of IP administration	Patients will take the melatonin or placebo for 14 days
Population	Sample size will be 252 patients, both male and female patients will be included, all adult patients undergoing primary elective TKA or THA will be included. No vulnerable populations will be enrolled
Study Sites	Langone Orthopedic Hospital, New York, NY NYU Brooklyn Hospital, Brooklyn, NY
Number of participants	256 participants
Description of Study Agent/Procedure	Melatonin is an over-the-counter sleep aid
Reference Therapy	None
Key Procedures	Pre- and postoperative sleep survey, survey on quality of sleep, patient reported outcome questionnaires, narcotic consumption and pain daily for 14 days postoperatively
Statistical Analysis	Descriptive statistics will be used to report baseline characteristics and primary study objectives

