### **8.4.2 Analysis of the Secondary Efficacy Endpoints**

The secondary endpoints include number of total hours of sleep, number of nighttime awakenings, and narcotic consumption.

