## **8.5 Measures to Minimize Bias**

### **8.5.1 Enrollment/Randomization/Masking Procedures**

Research assistants not involved in the study protocol will be responsible for maintaining the patient database and randomization algorithm. Treatment will begin on postoperative day zero. The control groups will receive 14 placebo pills. The treatment group will receive 14 pills of 5mg melatonin. Patients will begin taking a daily pill for 14 days postoperatively. They will continue to receive their selected treatment during their inpatient hospital stay.

Block randomization will be done through RedCap to ensure equal distribution of intervention vs control subjects. The block size will be undisclosed. There will be no stratification based on age, gender, or surgery type.

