#### **11.3.2 Consent Procedures and Documentation**

Informed consent is a process that is initiated prior to the individual's agreeing to participate in the study and continues throughout the individual's study participation. Extensive discussion of risks and possible benefits of participation will be provided to the participants and their families. Consent forms will be IRB-approved and the participant will be asked to read and review the document.

The informed consent process will take place at a pre-surgery clinic visit prior to the day of surgery or in the holding area on the day of surgery. If consenting occurs on the day of surgery, the study team will ensure that efforts are made so patients have enough time to make an informed decision to enroll in the study. A study coordinator, not associated with the surgery, will be the one to introduce the study to the patient in the holding area and patients will be given the opportunity to enroll in the study after the surgery is complete.

The Informed Consent Form (ICF) will be thoroughly explained in a private room with any and all questions addressed prior to signing the ICF. In the event additional time to make an informed decision is required, patient(s)/subject(s) will be able to take a copy of the ICF home for further review and discussion with their friends and family. During the course of the consenting process, subjects will interact with all study personnel. The participant will sign the informed consent document prior to any procedures being done specifically for the study. The participants may withdraw consent at any time throughout the course of the trial. A copy of the signed informed consent document will be given to the participants for their records. The rights and welfare of the participants will be protected by emphasizing to them that the quality of their medical care will not be adversely affected if they decline to participate in this study.

A copy of the signed informed consent document will be stored in the subject's research record. The consent process, including the name of the individual obtaining consent, will be thoroughly documented in the subject's research record. Any alteration to the standard consent process (e.g. use of a translator, consent document presented orally, etc.) and the justification for such alteration will likewise be documented.

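### The in-patient opioid count includes doses given after surgery but before the first study pill, which adds noise to a secondary endpoint

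*Combined protocol and SAP*

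**What the plan says.** All references are to the combined protocol and SAP.

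- **Opioid measure.** Section 6.1.1 states: "Opioid consumption will be measured based on in-patient pain medications given following surgery". On extraction it adds: "This data will be pulled from Epic following discharge". The count thus opens after surgery and closes at discharge. The schedule in section 6.2 also describes the item as in-patient opioid consumption.
- **A different window.** Under key procedures, the Protocol Summary lists "narcotic consumption and pain daily for 14 days postoperatively".
- **First pill.** Section 8.5.1 states: "Treatment will begin on postoperative day zero". All 14 pills are postoperative. Section 5.1.5 tells patients to "take one pill in the evening with water within 1 hour of bedtime each night for 14 days".
- **Late enrolment.** For patients approached in the holding area, section 11.3.2 says that "patients will be given the opportunity to enroll in the study after the surgery is complete".
- **Analysis.** Section 8.4.2 says only: "The secondary endpoints include number of total hours of sleep, number of nighttime awakenings, and narcotic consumption". It gives no window, unit, method or covariate for opioid use.

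**The concern.** Read together, these sections start the outcome before the treatment. Opioid given in recovery and on the ward before the first evening pill cannot respond to melatonin, yet it is added to opioid that can. For a patient who enrols after the operation, some of it may even precede enrolment. No section starts the count at the first dose, reports the earlier doses separately or adjusts for them.

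Opioid consumption is part of the stated study purpose and a secondary objective. Noise that treatment cannot influence makes a null result harder to interpret, and a percentage reduction in the total understates the reduction after treatment starts. The same early doses, if separated, would probably be a useful baseline covariate.

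**Working it through.** **The plan's own figure.** Section 8.2 gives 64 per arm per cohort for the Epworth score, from a difference of 2.65, SD 5.3, two-sided alpha 0.05 and 80% power. The normal approximation is 2 × (1.960 + 0.842)² × (5.3/2.65)² = 62.8, so 63. The two-sample t-test gives 63.77, so 64, with 80.1% power. The figure reproduces. It concerns the primary endpoint; no calculation is given for opioid use.

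**Order of events.** Surgery ends and the count opens (6.1.1). The first pill follows that evening (5.1.5, 8.5.1). Discharge closes the count (6.1.1). Sections 5.1.1 and 5.2 hand over the bottle before surgery, and sections 6.2 and 6.2.3 at surgery, but neither version creates an earlier dose.

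**Setup.** Let A be opioid from the end of surgery to the first pill, and B in-patient opioid after it. Let k = SD(A)/SD(B) and let rho be their correlation. The documents supply none of these, so the values below are assumptions.

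**Bias.** Randomisation makes the expectation of A equal in both arms. The expected difference in A + B is therefore the expected difference in B, and the test remains valid under the null.

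**Relative effect.** If a fraction f of the total is pre-pill, a 20% reduction in B appears in the total as 20% × (1 − f): 18% for f = 0.10, 15% for f = 0.25, 10% for f = 0.50.

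**Power.** In units of Var(B), Var(A + B) = 1 + k² + 2·rho·k. A 0.5 SD effect on B becomes 0.5/√(1 + k² + 2·rho·k) on the total. Two-sample t-test, 64 per arm:

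| k | rho | Var(A + B) | Effect (SD) | Power |
|---|---|---|---|---|
| 0 (count starts at pill) | – | 1.00 | 0.500 | 80% |
| 0.25 | 0 | 1.06 | 0.485 | 78% |
| 0.25 | 0.5 | 1.31 | 0.436 | 69% |
| 0.5 | 0 | 1.25 | 0.447 | 71% |
| 0.5 | 0.5 | 1.75 | 0.378 | 56% |
| 1 | 0 | 2.00 | 0.354 | 51% |
| 1 | 0.5 | 3.00 | 0.289 | 37% |

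**Plausible k.** Assume surgery ends 6 to 10 h before bedtime. The pre/post time ratio is then 6/42 = 0.14 to 10/38 = 0.26 for a 48 h stay, and 6/18 = 0.33 to 10/14 = 0.71 for a 24 h stay. If SD scales with time, k of 0.25 to 0.5 is a reasonable middle range. k = 1 requires heavier use in the first hours.

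**Covariate.** If B = a + b·arm + c·A + e, then A + B = a + b·arm + (1 + c)·A + e. The treatment estimate b and its standard error are identical. Once A is in the model, it makes no difference to the absolute comparison whether A is also left in the outcome.

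**The case against.** The strongest reply is that the start of the window is a detail of a larger gap. Section 6.1.1 names a data source, section 8.4.2 names an endpoint without a window, and the Protocol Summary promises 14 days of daily data. That stands: the window has to be defined as a whole, and the early hours are one part of it. In a 14-day record starting after surgery, 6 to 10 h is only 6/336 to 10/336, about 2 to 3% of the time (more if use is front-loaded). The problem matters mainly for the short in-patient count.

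Four stronger readings are tempting, and the documents do not support them.

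- A reader might infer that the comparison is biased. It is not: only precision and relative measures suffer, and the plan specifies no percentage measure for opioid use.
- A reader might set the unadjusted total against post-pill opioid adjusted for the pre-pill amount, and find power falling from 80% to between 57% and 19% (k of 0.5 to 1, rho of 0.3 to 0.7). That charges the window start with the loss from a missing covariate. At rho = 0.5 and k = 0.5, 80% with adjustment is already 68% for unadjusted post-pill opioid, so the loss due to the start is 68% to 45%.
- A reader might infer that for patients sent home before bedtime on the day of surgery the whole count is pre-treatment. That follows arithmetically, but no section describes such discharges. Section 6.1.2 lists an in-patient stay, and section 8.5.1 has treatment continuing through it.
- A reader might infer that much of the counted opioid precedes enrolment. The section 6.2 schedule places consent at Visit 1; section 11.3.2 opens the later route only to patients approached on the day of surgery.

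**Conclusion.** The point holds as a matter of precision. As written, the in-patient opioid endpoint includes doses that precede treatment, and nothing in the plan removes, separates or adjusts for them. The 78% to 56% power range depends on the assumed 0.5 SD effect and on the assumed k and rho; none of these can be checked against the documents. The loss could be smaller for longer stays, and it grows if early use dominates (51% to 37% at k = 1).

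The endpoint is secondary and the trial is not powered for it, so this is a cheap improvement rather than a threat to the trial. The Epworth comparison over days 1 to 14 is untouched.

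**What to change.** 1. In sections 6.1.1 and 8.4.2, state that Epic administration times will be used to split in-patient opioid at one pre-specified clock time on the evening of surgery, the same in both arms.
2. Analyse opioid after that time, with the earlier post-surgical amount as a baseline covariate. Keeping the total and adjusting for the earlier amount gives the same absolute treatment estimate and standard error.
3. Report by arm any patients discharged before the cut-off, whose in-patient record holds no later opioid.
4. Do not specify a window of equal length for everyone unless opioid use after discharge is collected. Discharge times differ, and length of stay is itself a secondary objective (section 2.1).
5. Reconcile the 14-day daily window in the Protocol Summary with the in-patient measure in sections 6.1.1 and 6.2.

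The cost is wording and one extra time field in an extraction already planned. The limitation is that section 5.1.5 ties the pill to each patient's own bedtime, so a common clock time only approximates the first dose.
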